5.4.3 Excluded Medications/Products and Foods

Subjects will be asked to refrain from consuming all over-the-counter medications and dietary supplements (vitamins, minerals and/or other supplements) within 3 d prior to visit 1 (day -7) and/or prescription medications (except for stable-dose oral contraceptives) within 14 d prior to visit 1 (day -7) and throughout the study period. For females on oral contraceptives, the subject must be on a stable dose of oral contraceptives (defined as same dose for the past 90 d prior to Visit 1; day -7). Additionally, subjects will avoid grapefruit and/or grapefruit juice within 3 d of all test visits (Visits 2, 3, and 4; days 0, 7, and 14). Should a subject require any of these medications or supplements, the study staff should consult with the Project Manager to discuss the subject's continued participation in the trial.

5.4.4 Enrollment

If a subject meets all inclusion and none of the exclusion criteria, a staff member will select the next sequential enrollment number for the subject. The enrollment number will

be recorded with the subject's source documentation. The total sample population will include 50% women with the goal of completing a minimum of 6 subjects.

5.5 Study Products

5.5.1 Description

- Low dose (170 mg Sr) strontium *L*-lactate
- Medium dose (340 mg Sr) strontium L -lactate
- High dose (680 mg Sr) strontium L -lactate

The study product will be provided as a dry powder packaged in individual vials. The study product will be prepared for consumption by dissolving the dry powder in the vial by adding 10 mL of distilled water and stirring the mixture. This liquid mixture will then be poured into an administration cup. An additional 10 mL of distilled water will be used to rinse the remaining study product into the administration cup. The remaining 80 mL of distilled water will be added directly into the administration cup. Following subject consumption of the 100 mL distilled water (with dissolved study product powder), another 100 mL will be added into the administration cup, swirled, and consumed by the subject. Study product information may be found in Appendix 5.

5.5.2 Labeling and Packaging

The Sponsor will provide pre-packaged, sealed, study product, each item labeled with the protocol number, dose, expiration date, and the statement "For Investigational Use Only."

5.5.3 Storage and Dispensing

Study products will be stored in a cool, dry, secure location at ambient temperature. Study product supplies are to be used only in accordance with this protocol and under the supervision of the Clinical Investigator. All records must be available for inspection by the Sponsor and are subject to regulatory agency inspection at any time. Copies of the records will be provided to the Sponsor at the conclusion of the study. A written explanation from the study staff will be required for any missing study product.

5.6 Clinical Measurements

5.6.1 Clinic Visit Procedures

Clinic visits will include assessment of height (Visit 1; day -7 only), body weight (Visits 1 through 4; days -7 to 14), BMI (Visit 1; day -7 only), evaluation of prior and concomitant medication/supplement use, and a review of inclusion/exclusion criteria (for eligibility at Visit 1 and for potential protocol deviations at subsequent visits).

Standardized vital signs measurements will be assessed at each clinic visit (Visits 1 through 4; days -7 to 14) and will include resting blood pressure and heart rate measured using an automated blood pressure measurement device. Blood pressure will be obtained after the subject has been sitting for at least five min. Systolic and diastolic pressures will be measured once using an appropriate sized cuff (bladder within the cuff must encircle ≥80% of the arm). Clinic staff may take a second blood pressure and heart rate,

if warranted. In the event a second measure is assessed; the second measurement will be recorded in the eCRF. Should elevated blood pressure be present at the screening visit (Visit 1; day -7), one retest will be allowed on a separate day, prior to Visit 2 (day 0).

5.6.2 Laboratory Measurements

The procedures for all clinical laboratory measurements will be outlined in a laboratory instruction sheet. **Lab**oratory parameters that are missing or have not been obtained must be entered in the eCRF as "not done."

The FDA-approved glucometer, with test strips from the same lot, will be used for determination of the in-clinic (Biofortis Clinical Research, Addison, IL) fasting capillary blood glucose (mmol/L) at Visits 1, 2, 3, and 4 (days -7, 0, 7, and 14) to ensure adequate fasting (10-14 h). Visits may be rescheduled for non-compliance, in the judgment of the Clinical Investigator.

The following will be performed as a part of the fasting (10-14 h) chemistry profile at Visit 1 (day -7): glucose, sodium, potassium, chloride, carbon dioxide, BUN, creatinine, calcium, osmolality, AST, ALT, ALP, total bilirubin, total protein, and albumin. Analytes will be assessed by Elmhurst Memorial Reference Laboratory (Elmhurst, IL).

The following will be performed as part of the fasting (10-14 h) hematology measurements at Visit 1 (day -14): WBC, RBC, hemoglobin concentration, hematocrit (as volume percent), MCV, MCH, MCHC, neutrophils, lymphocytes, monocytes, eosinophils, basophils and platelet count. Analytes will be assessed by Elmhurst Memorial Reference Laboratory (Elmhurst, IL).

Blood samples for the PK analysis of serum strontium will be collected at Visits 2, 3 and 4 (days 0, 7, and 14) at t = -0.25 h (\pm 10 min) and $t = 1, 2, 3, 4, 5, 6, 8, 10, and 12 h (<math>\pm$ 5 min), where t = 0 h is the start of study product consumption. Analytes will be assessed by NMS Labs (Willow Grove, PA). Additional samples will be stored as backup in the event the original sample is not viable.

An in-clinic urine pregnancy test will be performed on all women <60 years of age at Visit 1 (day -7).

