Stratum $Plus^{TM}$, is a highly pure form of strontium L-lactate (the strontium salt of L-lactic acid). Stratum Plus is manufactured in compliance with current Good Manufacturing Practices. The product has been thoroughly tested and meets rigorous purity specifications. It is free from contamination by D-lactic acid and trace metals known to harm human health. Unlike strontium renalate (and other related strontium salts), no clinical trials have been conducted with Stratum Plus. Thus, this study will be conducted to obtain pharmacokinetic (PK) information following acute oral intakes of three doses of Stratum Plus in healthy adults.

3. Objectives

The objective of this clinical trial is to obtain PK information following acute oral intakes of three doses of Stratum Plus in healthy adults.

4. Study Sample Population

Subjects will be healthy men and women 18-65 years of age, inclusive, with a body mass index (BMI) 18.0 to 31.9 kg/m². Subjects must also exhibit a body weight >60 kg, inclusionary.

5. Study Design and Procedures

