At Visit 2 (day 0), subjects will arrive at the clinic fasted (10-14 h, water only, anchored to the t = -0.25 h blood draw) for the 12-h PK test visit. Subjects will undergo clinic visit procedures including: a review of inclusion/exclusion criteria, concomitant medication/supplement use, body weight, and vital signs assessment. Adverse events (AE) will be assessed and subjects will be queried about study instructions compliance. Additionally, the 24-h Diet Record will be collected and reviewed. A fasting capillary blood glucose will be assessed to confirm fasting status. Eligible subjects will be enrolled and will begin the PK test with the insertion of an intravenous catheter at least 5 min prior to the first blood sampling time. In order to maintain patency of the intravenous catheter, the catheter will be flushed with normal saline solution at least hourly. Blood samples will be drawn by venipuncture if the catheter fails. Blood samples will be obtained at $t = -0.25 \text{ h} \pm 10 \text{ min}$ for the PK analysis of serum strontium, where t = 0 h is the time of study product consumption. Additional blood samples will be collected at all timepoints for backup. Subjects will consume the study product in its entirety within 10 min at t = 0 h. The study product will be dissolved with 100 mL of distilled water with an additional 100 mL of distilled water consumed immediately following. No food will be ingested for the subsequent 2-h period, but ad libitum water consumption will be allowed for the remainder of the visit following study product consumption. Water consumption will be recorded at the subsequent test visits. Blood samples will be obtained for the PK analysis of serum strontium at t = 1 and $2 h \pm 5$ min, where t = 0 h is the start of study product consumption. Subjects will be administered a standard breakfast immediately following the t = 2 h blood draw. Subjects will consume the breakfast meal in its entirety within 30 min.

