Blood samples will be obtained via the indwelling venous catheter or venipuncture at t=3,4,5,6, and $8 \text{ h} \pm 5 \text{ min}$, where t=0 h is the start of study product consumption, for the PK analysis of serum strontium. Subjects will be administered a standard lunch (immediately following the t=6 h blood draw), a standard snack (immediately following the t=8 h blood draw) and a standard dinner (at t=10 h). Subjects will consume the meals/snack in their entirety within 30 min. Following the final blood draw at $t=12 \text{ h} \pm 5 \text{ min}$, AEs will be assessed. Subjects will be dispensed a blank/new 24-h Diet Record to record all food and beverage consumed the day prior to Visit 3 (day 7); as well as a copy of the completed 24-h Diet Record (from day -1) with instructions to replicate the same food and beverage intake as closely as possible the day prior to the subsequent visit. Study instructions will also be provided [(i.e., fasting compliance (10-14 h, water only) and avoidance of alcohol 3 d prior to the subsequent test visits].

At Visits 3 and 4 (days 7 and 14), subjects will return to the clinic for clinic visit procedures (i.e., vital signs; body weight; review inclusion and exclusion criteria for relevant changes, and concomitant medication/supplement use review). AEs will be

assessed and subjects will be queried about study instructions compliance. The 24-h Diet Record will be collected and study staff will review the 24-h Diet Record to compare food and beverage consumption to the day -1 recall for consistency. If the subject's food intake is not consistent from the 24-h Diet Record reviewed at Visit 2 (day 0), the study staff should contact the Project Manager before continuing the visit as the test visit may require rescheduling. Subjects will then crossover to the next sequential dose of study product [medium dose at Visit 3 (day 7) and high dose at Visit 4 (day 14)] and repeat the PK test described above for Visit 2.

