5.3 Flowchart

			Test Days	
	Screening	Low Dose	Medium Dose	High Dose
Visit ¹	1	2	3	4
Days	-7	0	7	14
Informed Consent/HIPAA ²	X			
Clinic Visit ³	X	X	X	X
Medical History	X			
Chemistry Profile ⁴	X			
Hematology Panel ⁵	X			
In-clinic Urine Pregnancy Test ⁶	X			
Vein Access Scale Assessment ⁷	X			
Study Instructions/Query ⁸	X	X	X	X
Enrollment		X		
Capillary Glucose ⁹	X	X	X	X
Dispense 24-h Diet Record ¹⁰	X	X	X	
Collect/Review/Copy 24-h Diet Record ¹¹		X	X	X
Pharmacokinetic Test ¹²		X	X	X
Backup Blood Samples ¹³		X	X	X
Adverse Event Assessment ¹⁴		X	Х	X

Footnotes:

¹ A period up to 21 d will be allowed between Visits 1 and 2 (days -7 to 0) and the washout period between Visits 2 and 3 (days 0 and 7) and Visits 3 and 4 (days 7 and 14) will be 6-13 d.

³Clinic visit procedures include measurement of height (Visit 1 only), body weight, BMI (first visit only), vital signs, and where appropriate, a review of inclusion/exclusion criteria (for eligibility at Visit 1 and for potential protocol deviations at subsequent visits), and concomitant medication/supplement use.

⁴The following will be performed as part of the fasting (10-14 h) chemistry profile: albumin, alkaline phosphatase, total bilirubin, direct bilirubin, calcium, chloride, creatinine, blood urea

² Health Insurance Portability and Accountability Act (HIPAA) for disclosure of protected health information. Signed document authorizes the use and disclosure of the subject's Protected Health Information by the Investigator and by those persons who need that information for the purposes of the study.

nitrogen (BUN), potassium, aspartate aminotransferase (AST), alanine aminotransferase (ALT), sodium, total protein, carbon dioxide (CO₂), osmolality, and glucose.

⁵The following will be performed as part of the fasting (10-14 h) hematology panel: white blood cell count (WBC), red blood cell count (RBC), hemoglobin concentration, hematocrit (as volume percent), mean cell volume (MCV), mean cell hemoglobin (MCH), mean cell hemoglobin concentration (MCHC), neutrophils, lymphocytes, monocytes, eosinophils, basophils and platelet count.

⁷Appendix 2.

¹⁰Subjects will complete a 24-h Diet Record identifying all food and beverages consumed the day prior to Visit 2 (day 0; Appendix 3). A clean copy of the 24-h Diet Record will also be provided with instructions for subjects to complete the record the day prior to Visits 3 and 4.

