5.4 Study Sample

Each subject must meet all of the following inclusion criteria and none of the exclusion criteria at baseline (Visit 2, day 0) in order to participate in this study.

⁶ To be completed on all women <60 years of age.

⁸ Subjects will be instructed to fast for 10-14 h and to avoid of alcohol 3 d prior to test visits. Subjects will be queried about compliance with these instructions.

⁹Capillary glucose concentrations will be measured at each clinic visit using an FDA-approved glucometer to ensure adequate fasting (10-14 h). Visits may be rescheduled for non-compliance, in the judgment of the Clinical Investigator.

¹⁴Inquiring about AEs will occur with an open-ended question at the beginning and end of study visits.

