- 12. Subject is a female, who is pregnant, planning to be pregnant during the study period, lactating, or is of childbearing potential and is unwilling to commit to the use of a medically approved form of contraception throughout the study period. The method of contraception must be recorded in the source documentation.
- 13. Subject has been exposed to any non-registered drug product within 30 d prior to visit 1 (day -7).
- 14. Subject has a recent history of (within 12 months of screening; Visit 1; day -7) or strong potential for alcohol or substance abuse. Alcohol abuse is defined as >14 drinks per week (1 drink = 12 oz beer, 5 oz wine, or 1½ oz distilled spirits).
- 15. Individual has a condition the Clinical Investigator believes would interfere with his or her ability to provide informed consent, comply with the study protocol, which might confound the interpretation of the study results, or put the subject at undue risk.

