7.3.7 Pregnancy

There are no adequate and well-controlled studies on strontium L-lactate use in pregnant women, therefore, pregnant or lactating women will be excluded from the study. Additionally, the outcome variables measured would be expected to be affected by pregnancy and lactation. All female participants <60 years of age will undergo in-clinic urine pregnancy testing at Visit 1 (day -7). Pregnant or lactating women will be excluded from the study and women of childbearing potential will be required to use appropriate contraceptive methods to avoid pregnancy. Documentation of contraception method must be recorded in the source chart.

Although pregnancy is not a SAE, all pregnancies occurring in enrolled subjects will be reported within 24 h of notification. The Clinical Investigator will immediately notify the Sponsor, the Project Manager and the IRB about the pregnancy. Should a female subject become pregnant at any time after randomization the Clinical Investigator will be required to follow the subject through the pregnancy term and report to Biofortis Innovation Services the course of the pregnancy including perinatal and neonatal outcomes.

8. Conduct of the Study

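### Pregnancy must be excluded at Visit 2, but the only pregnancy test is at Visit 1, 7 to 21 days before the first dose; repeat the urine test at Visit 2 before enrollment and dosing.

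*Combined protocol and SAP*

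**What the plan says.** Section 5.6.2 (Laboratory Measurements) states "An in-clinic urine pregnancy test will be performed on all women" younger than 60, at Visit 1 (day -7). The Visit 1 narrative in section 5.2, the flowchart in section 5.3, the screening list in section 5.7.1 and section 7.3.7 (Pregnancy) agree. The test does not appear in the Visit 2 narrative, the test-day schedule in section 5.6.6 or the test-visit list in section 5.7.2.

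Eligibility is fixed at a later date. Section 5.4 reads: "Each subject must meet all of the following inclusion criteria and none of the exclusion criteria at baseline (Visit 2, day 0"). Exclusion 12 in section 5.4.2 begins: "Subject is a female, who is pregnant, planning to be pregnant during the study period, lactating". It goes on to exclude women of childbearing potential who will not commit to approved contraception during the study. Section 5.2 places enrollment at Visit 2, immediately before the pharmacokinetic test.

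On timing, footnote 1 of the flowchart says: "A period up to 21 d will be allowed between Visits 1 and 2". The same footnote sets each washout at 6 to 13 days.

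On the reasons for excluding pregnancy, section 7.3.7 notes the lack of adequate studies of strontium L-lactate in pregnant women and adds that "the outcome variables measured would be expected to be affected by pregnancy and lactation". The background section says that "no clinical trials have been conducted with Stratum Plus".

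After Visit 1 the plan relies on checks that involve no test. Visit 2 includes "a review of inclusion/exclusion criteria, concomitant medication/supplement use, body weight, and vital signs assessment"; at Visits 3 and 4 staff "review inclusion and exclusion criteria for relevant changes". Section 7.3 adds an open question about changes in health or medication.

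**The concern.** The eligibility rule applies on the day of dosing, but the only measurement bearing on exclusion 12 is made at screening. Some other criteria are tied explicitly to Visit 1: vein access, weight and BMI (inclusions 2 and 3), laboratory results and blood pressure (exclusions 1 and 10). Pregnancy is not. A pregnancy too early to detect at Visit 1, or one that begins afterwards, would go unnoticed before dosing unless the woman already knew of it.

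The checks in between cannot close that gap. A criteria review and a health question depend on what the subject knows. Section 5.6.1 and flowchart footnote 3 also describe the reviews after Visit 1 as a search for protocol deviations, although section 5.4 makes Visit 2 the eligibility date. The contraception commitment in exclusion 12 covers the study period and does not reach back before Visit 1. Section 5.4.3 asks for 90 days on a stable dose, but only from women who use oral contraceptives. A conception shortly before Visit 1 can therefore pass both the test and the contraception rule.

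At stake is the exposure of an unrecognized pregnancy to up to three rising doses (170, 340 and 680 mg Sr) of a product not previously studied in a trial. This is a gap in verification. The sections do not contradict one another on when the test is done.

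**Working it through.** **Inputs**
- Pregnancy test: Visit 1 only, nominal day -7 (sections 5.6.2 and 7.3.7).
- Doses: Visits 2, 3 and 4, nominal days 0, 7 and 14 (section 5.2).
- Visit 1 to Visit 2: at most 21 days (flowchart footnote 1).
- Washout: 6 to 13 days each (same footnote). Section 5.2 pairs visits 7 days apart with a washout of at least 6 days, which suggests that the washout excludes a visit day and that visits may be up to 14 days apart. If 13 days is the visit interval itself, the maximum is 13. Both readings are carried through.
- Women: 10 subjects with about equal numbers of each sex (section 6.2), so 10 × 0.5 = 5.

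**Age of the only test at dosing, current plan**
- First dose: nominal 0 − (−7) = 7 days; maximum 21 days.
- Last dose (680 mg): nominal 7 + 7 + 7 = 21 days; maximum 21 + 13 + 13 = 47 days, or 21 + 14 + 14 = 49 days.

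**With a Visit 2 test before dosing**
- First dose: 0 days.
- Last dose: nominal 7 + 7 = 14 days; maximum 13 + 13 = 26 days, or 14 + 14 = 28 days.

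**Expected conceptions**

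The documents give no pregnancy rate. The assumption is 1 to 10% per woman-year under the required contraception, with all 5 women able to conceive. The formula is women × days / 365.25 × rate.

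| Interval | Days | Woman-years | Expected conceptions |
|---|---|---|---|
| Visit 1 to Visit 2, nominal | 7 | 5 × 7 / 365.25 = 0.096 | 0.001 to 0.010 |
| Visit 1 to Visit 2, maximum | 21 | 5 × 21 / 365.25 = 0.287 | 0.003 to 0.029 |
| Visit 1 to last dose, nominal | 21 | 0.287 | 0.003 to 0.029 |
| Visit 1 to last dose, maximum (47 d) | 47 | 5 × 47 / 365.25 = 0.643 | 0.006 to 0.064 |
| Visit 1 to last dose, maximum (49 d) | 49 | 5 × 49 / 365.25 = 0.671 | 0.007 to 0.067 |

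Three limits apply. The figures are too high if some women under 60, or among those aged 60 to 65, cannot conceive. They leave out conceptions just before Visit 1, the group a Visit 2 test is best placed to find. They count conceptions, not pregnancies that a urine test on day 0 would detect.

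**The case against.** The other side has a reasonable case. The plan is consistent: every section that mentions the test puts it at Visit 1, the protocol goes to an IRB, and nothing in the documents sets a maximum interval from test to dose. The Visit 2 rule covers every criterion, yet chemistry and hematology are not repeated either, so the plan can be read as testing at screening and reviewing thereafter. Women planning pregnancy or declining contraception are excluded, and any pregnancy must be reported within 24 hours and followed to outcome. A Visit 2 test can also miss a very recent conception, so an interval of 0 days does not prove that a woman is not pregnant. Finally, the remedy leaves a longer interval before the highest dose to local judgement.

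Much of this stands. The absolute risk is tiny, the added test detects only some cases, and most of the expected conceptions up to the last dose fall after Visit 2 when the intervals are nominal or at their maximum. Two points remain. Reporting and follow-up act after exposure, and none of the earlier safeguards can find a pregnancy the woman does not know about. The comparison with other criteria is also incomplete, because the plan does repeat an objective check where it wants assurance on the day: capillary glucose is measured at every test visit to confirm fasting. Leaving Visits 3 and 4 to the investigator and IRB limits the benefit but does not cancel it at the visit where eligibility is decided.

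**Conclusion.** The concern holds. The protocol requires pregnancy to be absent at Visit 2 but tests for it only at Visit 1, so the result may be three weeks old when the first dose is given. The date arithmetic follows directly from the schedule; only the 47 versus 49 day maximum depends on how the washout is counted.

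The likelihood is low: 0.001 to 0.010 expected conceptions between Visits 1 and 2 at the nominal gap and 0.003 to 0.029 at the maximum, on the assumed rate and 5 women. There is no effect on sample size, power or error rates, since section 6.2 makes no formal calculation and section 6.5 plans descriptive summaries only. The recommendation rests on subject safety with an untested product and on the very small cost of the check. The sponsor should make the change.

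**What to change.** Keep the Visit 1 test. In section 5.6.2, add that the urine test is repeated at Visit 2 (day 0) in all women under 60, and that a negative result is needed before a subject is enrolled and given study product. Carry the change into:
- the Visit 2 narrative in section 5.2;
- the pregnancy-test row and footnote of the flowchart in section 5.3;
- the test-day schedule in section 5.6.6, in the t = -1.0 h slot ahead of enrollment and catheter insertion;
- the test-visit list in section 5.7.2, for Visit 2;
- section 7.3.7.

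Whether to repeat the test before dosing at Visits 3 and 4 can be left to the investigator and IRB. Without it, the last dose still follows the Visit 2 test by nominally 14 and at most 26 to 28 days.

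The cost is protocol wording and about five more in-clinic urine tests, with no new staff, equipment or visits. The one drawback is that a subject could be found ineligible on the first test day.
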